6.3. Concomitant Treatments

- Concomitant medication status will be presented in frequency and percentage.
- Concomitant drugs classified by latest version of ATC code will be presented in n, percentage and frequency.

6.4. Safety Analyses

Safety analyses will be performed based on data of safety analysis set. All adverse events in CRF will be classified by System Organ Class (SOC) and Preferred Term (PT) according to the latest version of MedDRA.

- 1) All adverse events investigated after administration of Xeljanz® during the study will be summarized by frequency and percent (n, percentage) by categorizing as follows. Also, it will be presented in n, incidence rate, 95% confidence interval of incidence rate and number of events for each SOC and PT.
 - Frequency analysis of adverse events/adverse drug reactions
 - Frequency analysis of serious adverse events/serious adverse drug reactions
 - Frequency analysis of serious unexpected adverse events/serious unexpected adverse drug reactions
 - Frequency analysis of unexpected adverse events/unexpected adverse drug reactions
 - Frequency analysis of adverse events of special interest/adverse drug reactions of special interest
 - Occurrence status of adverse events/adverse drug reactions by its seriousness
 - Results in death
 - Is life-threatening
 - Requires inpatient hospitalization or prolongation of hospitalization
 - Results in persistent or significant disability/incapacity
 - Results in congenital anomaly/birth defect
 - Important medical event: if it is determined that the event may jeopardize the patient or may require intervention to prevent one of the other outcomes listed in the definition above
 - Occurrence status of adverse events/adverse drug reactions by its severity
 - Mild
 - Moderate
 - Severe
 - Occurrence status of adverse events/adverse drug reactions by its causality assessment
 - Related to this medicinal product: ① Certain

Statistical Analysis Plan

- ② Probable/likely
- ③ Possible
- ⑤ Conditional/unclassified
- ⑥ Unassessable/unclassifiable

- Not related to this medicinal product: ④ Unlikely
- Occurrence status of adverse events/adverse drug reactions by its action taken
 - Permanently discontinued
 - Temporarily discontinued or delayed
 - Dose reduced
 - Dose increased
 - No change
 - Not applicable
- Occurrence status of adverse events/adverse drug reactions by its outcome
 - Recovered
 - Recovered with sequelae
 - Recovering
 - Not recovered
 - Unknown

2) Occurrence status of adverse events by demography and baseline characteristics

Occurrence status of adverse events will be presented in frequency and percentage and incidence rate with 95% confidence interval based on categorical variables of demography and baseline characteristics of the patients. To identify statistically significant difference in occurrence of adverse events by demography and baseline characteristics, Chi-square test or Fisher's exact test will be performed.

3) Occurrence status of adverse events by concomitant treatment

Occurrence of adverse events will be presented in frequency and percentage and incidence rate of adverse events with 95% confidence interval by concomitant treatment status. To identify statistically significant difference in occurrence of adverse events by concomitant treatment status, Chi-square test or Fisher's exact test will be performed.

4) Analysis of factors that affect the safety

In the re-examination report, logistic regression analysis of multivariate analysis will be performed and presented an odds ratio with 95% confidence interval to identify the factors that affect occurrence of adverse events in demography and baseline characteristics, or concomitant treatment status, etc.

5) Distribution for special patient populations (elderly (age over 65 years old), renal disorder, hepatic disorder) will be presented. Also, adverse events and adverse drug reactions collected

Statistical Analysis Plan

by these groups will be presented in incidence rate and number events of it for each SOC and PT.

[figure not shown]
- For children and pregnant women, it will be performed in off-label patient analysis because administration of children (age less than 19 years old) and pregnant women is contraindicated according to the local product document.

6) Distribution for off-label evaluation patients will be presented. Also, adverse events and adverse drug reactions collected by these groups will be presented in incidence rate and number events of it for each SOC and PT.

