### 7.2.5. Study procedures

The investigator should enroll all patients to whom Xeljanz is prescribed for the first time according to the local product document and who agree to participate in this study by signing the data privacy statement (used in place of the informed consent form) by continuous registration method. In case of the patients who already have been administered Xeljanz but not participated in this study, study related information from the first administration until the last day of the observation period should be collected retrospectively. Xeljanz tablets will be medicated by the investigator's prescription under usual clinical practice. Pfizer Korea will not provide the medicinal product for this study.

There will be no mandatory visit during the study. The investigators will collect relevant data from the time of initiating administration of Xeljanz until 6 months of treatment. If the patient does not complete 6 months of treatment, relevant data should be collected based on the last assessment performed at the time of treatment discontinuation. The investigator should record the following information on the patient's CRF:

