##### **7.3.1.1. Adverse events**

Please refer to [Section 9](#) for the definition of non-serious and serious adverse events (SAEs).

Any AEs observed and reported within the reporting period will be recorded on the CRF by the investigator, regardless of the causal relationship with Xeljanz (see [Section 9.2](#)). The AEs can be reported by the patients. The investigator will also collect AE data by asking the patient questions such as “Have you had any health problem since the last visit?”

Check either “yes” or “no” in the AE section of CRF. If “yes”, record the following information:

Event name: Record the name of the AE according to the Korean Version of World Health Organization - Adverse Reaction Terminology (WHO-ART) distributed by Korean Ministry of Health and Welfare. If there is no not an appropriate term in the WHO-ART, record the name of the AE according to the Medical Terminology Dictionary written by the Korean Medical Society. If possible, specify diagnosis, not individual symptoms.

Date of onset: Record the onset date of the AE. Record approximate date if an actual date is unknown.

Date of recovery: Record the stop date of the AE if the outcome of the AE is recovered or recovered with sequelae (see below). Record approximate date if an actual date is unknown.

Seriousness: Check either “yes” or “no” to indicate if the event is a SAE. If “yes” record appropriate category of the seriousness (see [Section 9](#) for the definition and reporting of SAEs).

**Severity:** Evaluation of AE severity must be done according to the following categories:

- Mild: Not causing any significant problem to the patient. Administration of medicinal product continues without dose adjustment.
- Moderate: Causes a problem that does not interfere significantly with usual activities or the clinical status. Dose of the medicinal product is adjusted or other therapy is added due to the AE.
- Severe: Causes a problem that interferes significantly with usual activities or the clinical status. The medicinal product is stopped due to the AE.

If the severity of an AE changes, the AE must be entered separately. Record the stop date of the previous severity and onset date of the new severity – along with completion of all other related items.

**Causality assessment:** The causal relationship of AEs to the medicinal product must be allocated by the investigator according to the following criteria in alignment with the requirements of MFDS:

- Certain

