## **7.4. Data sources**

### **7.4.1. Case report forms**

As used in this protocol, the term CRF should be understood to refer to either a paper form or an electronic data record or both, depending on the data collection method used in this study.

A CRF is required and should be completed for each included patient. The completed original CRFs are the sole property of Pfizer and should not be made available in any form to the third parties, except for authorized representatives of Pfizer or appropriate regulatory authorities, without written permission from Pfizer. The investigator shall ensure that the CRFs are securely stored at the study site in encrypted electronic form and will be password protected to prevent access by unauthorized third parties.

The investigator has ultimate responsibility for the collection and reporting of all clinical, safety, and laboratory data entered on the CRFs, any other data collection forms (source documents) and ensuring that they are accurate, authentic/original, attributable, complete, consistent, legible, timely (contemporaneous), enduring, and available when required. The CRFs must be signed by the investigator or by an authorized staff member to attest that the data contained on the CRFs are true. Any corrections to entries made on the CRFs or source documents must be dated, initialed and explained (if necessary) and should not obscure the original entry.

In most cases, the source documents are the hospital's or the physician's patient chart. In these cases data collected on the CRFs must match the data in those charts.

In some cases, the CRF may also serve as the source document. In these cases, a document should be available at the investigator site and at Pfizer that clearly identifies those data that will be recorded on the CRF, and for which the CRF will stand as the source document.

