## **7.7. Data analysis**

Analysis will be performed for the pooled data collected by each investigator during the re-examination period. Total number of centers participating, total number of cases enrolled and retrieved, and total number of cases included in the analysis will be presented in summary tables. Evaluation of data will primarily consist of summary displays (eg, descriptive statistics, tables, and graphs).

Detailed methodology for summary and statistical analyses of data collected in this study will be documented in a Statistical Analysis Plan (SAP), which will be dated, filed and maintained by Pfizer. The SAP may modify the plans outlined in the protocol; any major modifications of primary endpoint definitions or their analyses will be reflected in a protocol amendment.

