2.2. Study Design

2.2.1. General Study Design

This is an open-label, non-comparative, non-interventional, prospective, and multi-center study conducted in Korean health care centers by accredited physicians (ie, investigators). The study population will be adult patients with moderately to severely active RA who have had an inadequate response or intolerance to methotrexate. Xeljanz® will be administered according to the "Dosage and Administration" of the approved labeling. There is no visit or activity mandated by this study. The investigator will collect patient data and record the information on each patient's case report form (CRF).

Statistical Analysis Plan

CCI

Also, investigators collect data on the Xeljanz retrospectively from the subjects who have been administered the Xeljanz according to the local product documents but not participated in this study for 2 years after completion of re-examination.

Safety is the primary interest of this study, which will be assessed based on adverse events (AEs) that occur during the 6 months from the first dose of Xeljanz®. The efficacy endpoints will be the modified Disease Activity Score using 28 joint counts (DAS28) change from baseline, European League Against Rheumatism (EULAR) response, and American College of Rheumatology 20% improvement criteria (ACR20) response after treatment.

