6.6.2. Sub-group Analyses by PsA

- [6.4. Safety Analyses] - 1)
- [6.5. Efficacy Analyses] - 1), 2), 4)

7. Reporting Principles

All results of analysis will be reported table and graph to assist the understanding for the study results. Continuous variables will be summarized by descriptive statistics (n, mean, standard deviation, median, minimum and maximum) and categorical variables will be presented in frequency and percentage (n, %). Summary statistics including n, mean, standard deviation, median, minimum and maximum, frequency, etc will be reported to two decimal places using rounding off.

In case of statistical hypothesis testing, two-sided test will be conducted under 5% significance level and the p-value of each test result will be presented in the summary table. The p-values through the statistical test will be reported to four decimal place and if p-values smaller than 0.0001 will be written as '<0.0001'.

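### The SAP pools prospectively and retrospectively collected adverse events without separating or adjusting for collection mode, so pooled AE incidence may depend on the retrospective share

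*SAP*

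**What the plan says.** Safety is the primary interest in both documents, and in both it is "assessed based on adverse events (AEs) that occur during the 6 months from the first dose of Xeljanz" (SAP 2.2.1; Protocol 7.1 agrees).

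AEs reach the CRF by two routes:

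- **Prospective.** Patients may report events themselves, and Protocol 7.3.1.1 adds: "The investigator will also collect AE data by asking the patient questions such as", followed by an example about health problems since the previous visit.
- **Retrospective.** SAP 2.2.1 states: "Also, investigators collect data on the Xeljanz retrospectively from the subjects who have been administered the Xeljanz" without having taken part. For these patients Protocol 7.2.5 requires that "study related information from the first administration until the last day of the observation period should be collected retrospectively". Protocol 7.4.1 names the usual source: "In most cases, the source documents are the hospital's or the physician's patient chart".

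The analysis does not keep the routes apart. SAP 3.1 defines one safety set, SAP 3.4 defines subgroups by indication only, and the baseline list in SAP 4.1 has no entry for mode. SAP 6.4 item 1) gives AE incidence with 95% intervals for the whole set. Item 2) compares AE occurrence by baseline factor ("To identify statistically significant difference in occurrence of adverse events by demography and baseline characteristics, Chi-square test or Fisher's exact test will be performed"), item 3) does the same by concomitant treatment, and item 4) fits a logistic model for the re-examination report. None of these names mode. SAP section 7 sets the level: "In case of statistical hypothesis testing, two-sided test will be conducted under 5% significance level". SAP 2.2.2 and Protocol 7.2.3 say that the report for the risk management plan (RMP) will draw on both prospective and retrospective data.

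**The concern.** Asking a patient at each visit and reading a finished chart are different ways of measuring AEs. Minor events that nobody wrote down at the time can surface under questioning but are hard to recover from a record. If that happens here, the pooled incidence is a weighted average of two measurements. Its weight is the number of retrospective cases added, not anything about the patients' risk, and the 95% interval does not reflect this.

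The tests in items 2) and 3) are exposed as well. A factor that is more common among retrospective patients would appear protective merely because fewer of their events were recorded. A factor that is less common among them would appear harmful. With no table by mode, a reader of the report could not tell whether this had happened.

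**Working it through.** No figure in the plan bears on this. The study-size section is blacked out, and the retrospective share, AE rates and factor distributions are not given. The check is therefore a reading of the text plus an illustration on assumed inputs.

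**Is mode used anywhere?** I went through the visible analysis sets (SAP 3.1 to 3.5), endpoints (4.1 to 4.5), missing-data rules (5.1) and analyses (6.1 to 6.6). Mode appears in none of them. No blacked-out block is visible in SAP 4.1 or 6.1 to 6.4. The exclusion in SAP 3.1 of patients enrolled and completed before the site contract might remove some retrospective cases, but it does not separate the modes.

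**Is different capture plausible?** For retrospective patients, consent or the privacy statement can be waived if the ethics committee so decides (Protocol 7.2.1 and 7.2.5.1), so some may never be contacted. Height and weight are taken only as ranges for them (7.2.5.2), which fits abstraction from records. Protocol 9.2 starts the safety reporting period of already exposed patients at the privacy statement, whereas 7.2.5 asks for information from first administration. That is a second way in which capture could differ.

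**Pooled incidence (assumed inputs).** Let p be the prospective incidence, c the fraction of events captured retrospectively and w the retrospective share:

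pooled = p × [(1 − w) + w × c]

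With p = 40%:

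| w | c = 0.5 | c = 0.7 | c = 1.0 |
|---|---|---|---|
| 10% | 38.0% | 38.8% | 40% |
| 30% | 34.0% | 36.4% | 40% |
| 50% | 30.0% | 34.0% | 40% |

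Any c below 1 makes the figure depend on w. With c = 1 the problem vanishes.

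**Factor test (assumed inputs).** Take a factor with no effect, N = 1,000, p = 30%, c = 0.5 (so 15% observed retrospectively) and w = 30%. Let 30% of prospective and 50% of retrospective patients carry the factor.

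- With factor: 700 × 0.3 = 210 prospective and 300 × 0.5 = 150 retrospective, n = 360. AE proportion = (210 × 0.30 + 150 × 0.15)/360 = 23.75%.
- Without factor: 490 and 150, n = 640. AE proportion = (490 × 0.30 + 150 × 0.15)/640 = 26.48%.
- Odds ratio = (0.2375/0.7625)/(0.2648/0.7352) = 0.86.
- Standard error = √[0.255 × 0.745 × (1/360 + 1/640)] = 0.0287, so the difference is 0.0273/0.0287 = 0.95 standard errors. A two-sided 5% test rejects with probability 15.9% (normal approximation).

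Varying one assumption at a time:

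- Factor balanced at 30% in both modes: odds ratio 1.00, rejection 5.0%.
- 30% against 40%: odds ratio 0.93, rejection 7.7%.
- c = 0.7: rejection 8.6%.
- N = 3,000: rejection 37.8%.

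Over the whole assumed range (w from 10% to 50%), rejection runs from 5% to 21% at N = 1,000 and up to 52% at N = 3,000. Within each mode the two groups have the same proportion (30% or 15%), so a mode-stratified test sees an odds ratio of 1 and stays near 5%.

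**The case against.** The strongest reply is about scope. Protocol 7.7 says "Analysis will be performed for the pooled data collected by each investigator", but the sentence goes on to limit this to the re-examination period, which ended on 01 April 2020. It describes pooling across investigators, not across modes. SAP 2.2.1 can be read as placing retrospective collection in the two years after that period. On that reading the re-examination report is wholly or largely prospective, and adding mode to the item 4) model would do nothing. This stands as a limit on the point. It does not remove it: retrospective collection entered the protocol in August 2019, before the period ended, items 1) to 3) are not confined to the re-examination report, and the RMP report is stated to use both modes.

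The contrast between modes can also be overdrawn. Neither mode has mandated visits, and charts are the usual source for every patient. Protocol 7.3.1.1 does not confine questioning to prospective patients, and a retrospective patient still in care could be asked, with the limits of recall. This stands too. Less complete capture is an inference from the text, not something it states.

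Finally, text next to the design and duration statements is blacked out, and some accounting by mode could lie there. That cannot be excluded, but the analysis sections where it would have to take effect are visible and do not contain it.

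**Conclusion.** The omission is confirmed in the visible text, and it touches the study's primary output. Its consequences are conditional. Bias in pooled incidence requires different capture. Distortion of the factor tests requires, in addition, a factor whose prevalence differs by mode. The percentages above show how the mechanism works under assumed inputs and do not estimate its size in this study.

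Three stronger readings are not supported:

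- **That ascertainment is confused with a drug effect.** The study has no comparator and estimates no drug effect. What is mixed with ascertainment is the AE risk, or a factor's association with it.
- **That the comparison of rheumatoid arthritis (RA) with psoriatic arthritis (PsA) will be biased in a known direction.** PsA came late (approved September 2018, added to the protocol in February 2019), which might raise its retrospective share. But PsA patients could be enrolled prospectively after that, and untreated-by-protocol RA patients had been accumulating since the 2014 approval. With assumed rates of 40% and 25%, and 20% of RA and 70% of PsA patients retrospective, the table shows 0.8 × 40 + 0.2 × 25 = 37.0% against 0.3 × 40 + 0.7 × 25 = 29.5%, an odds ratio of 1.40. Swapping the two shares gives 1/1.40 = 0.71. The direction is set by the assumption alone. SAP 6.6 also reports the two indications separately, though not by mode.
- **That the prospective figure is the right one to quote.** Patients who consent may themselves be selected, and nothing in the documents ranks one mode above the other.

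This is an inexpensive improvement worth making. It does not show that the results will be wrong.

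**What to change.** 1. Add data collection mode (prospective or retrospective) to the baseline variables in SAP 4.1 and to the summaries in 6.1.
2. In SAP 6.4 item 1), for any report that contains both modes and notably the RMP report, show overall AE, adverse drug reaction and serious AE incidence with 95% confidence intervals by mode beside the pooled figure. Label this a sensitivity analysis and do not declare one figure primary.
3. For items 2) and 3), add a sensitivity version of the tests, either stratified by mode (Cochran-Mantel-Haenszel) or restricted to prospective patients.
4. In item 4), include mode as a covariate if the re-examination data turn out to contain retrospective patients.

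No new data should be needed. The CRF already records age, height, weight and the privacy statement differently by mode, so mode should be identifiable for each patient. The cost is SAP wording, a few more tables and wider intervals within each mode. In the 1,000-patient illustration, the normal-approximation half-width is 1.96 × √(0.255 × 0.745/1000) = 2.7 points pooled, 1.96 × √(0.30 × 0.70/700) = 3.4 points prospectively and 1.96 × √(0.15 × 0.85/300) = 4.0 points retrospectively. If the two modes prove alike, the same table is how the sponsor would show it.

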#### **7.2.5.4. Concomitant treatments**

Any concomitant treatments should be recorded on the CRF for each patient. The information should include:

- Name of the drug: Record generic name of the concomitant medication.
- Daily dose: Record total daily dose of the concomitant medication.
- Duration of the treatment: Record the start date and stop date (year/month/day) of the concomitant medication. If the medication is being continued at the completion of the study, record the start date only and check “ongoing”.
- Purpose of the treatment: Record purpose of the concomitant treatment in detail.

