### **7.7.1. Safety analysis**

[figure not shown]
The primary interest of this study is the incidence of AEs investigated during the re-examination period. Incidence of each AE will be presented with 95% confidence interval. Serious, related, and/or unexpected AEs will be summarized separately.

To identify the factors that affect safety, subgroup analysis for various factors will be performed, including the classification of AEs by body system, and comparison of incidence of AEs by sex, age, presence of concurrent diseases, presence of concomitant medications, baseline disease activity, etc.

In case the drug was administered to special populations such as children, elderly people, or patients with renal or hepatic disorders during the study, subgroup analysis will also be performed for each of those populations.

Unexpected AEs/ADRs will be classified by medical review with reference to the local product document. Events already included in the “Precautions for use” section of the local product document will be classified as “expected”. All other events that are not included in the “Precautions for use” section of the local product document will be classified as “unexpected”. An unexpected AE includes any events that may be symptomatically and patho-physiologically related to an event listed in the labeling, but differs from the labeled event because of greater severity or specificity.

In the case of an adverse event with important potential risks and important identified risks in relation to the safety specification under the risk management plan, or if missing information patient group is recruited, actions according to the label will be taken, and the safety information is presented separately.

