#### Abnormal test findings

The criteria for determining whether an abnormal objective test finding should be reported as an AE are as follows:

- Test result is associated with accompanying symptoms, and/or
- Test result requires additional diagnostic testing or medical/surgical intervention, and/or
- Test result leads to a change in study dosing or discontinuation from the study, significant additional concomitant drug treatment, or other therapy, and/or
- Test result is considered to be an AE by the investigator or sponsor.

Merely repeating an abnormal test, in the absence of any of the above conditions, does not constitute an AE. Any abnormal test result that is determined to be an error does not require reporting as an AE.

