4.3. Concomitant Treatments

Assessment variable for concomitant treatments of patients will be included the following.

- Concomitant medication status
- Concomitant drugs classified by latest version of ATC code as level 1 and level 2

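### Concomitant treatment status in SAP 6.4(3)–(4) has no time window, so drugs given to treat an adverse event can make concomitant treatment look like a risk factor for it

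*SAP*

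**What the plan says.** SAP 4.3 introduces the variables with "Assessment variable for concomitant treatments of patients will be included the following" and lists a concomitant medication status and the ATC class of the drugs. It gives no time window, and SAP 6.3 adds none. SAP 6.4(3) then tests AE occurrence "To identify statistically significant difference in occurrence of adverse events by concomitant treatment status". SAP 6.4(4) plans a multivariable logistic regression, reporting odds ratios with 95% confidence intervals, to find "the factors that affect occurrence of adverse events in demography and baseline characteristics, or concomitant treatment status".

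The protocol has the same gap. Section 7.7.1 states the purpose, "To identify the factors that affect safety, subgroup analysis for various factors will be performed", and lists the presence of concomitant medications among the factors. In that list disease activity is qualified as baseline; medication is not.

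On data collection, Protocol 7.2.5.4 says "Any concomitant treatments should be recorded on the CRF for each patient", with the dates and purpose of each. Two passages show that AEs are expected to lead to new drugs:

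- The moderate severity grade in Protocol 7.3.1.1 includes "Dose of the medicinal product is adjusted or other therapy is added due to the AE".
- Under Protocol 9.4.1 (Abnormal test findings), one criterion that makes a test result an AE is that it leads to "significant additional concomitant drug treatment, or other therapy".

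**The concern.** With no window, the natural way to program the status is yes if any concomitant drug appears on the CRF. A patient who starts Xeljanz on no other drug, has an AE and is given something for it is then counted as exposed. A patient without an AE has no such route into the exposed group. The exposure is partly a consequence of the outcome, and this misclassification runs in one direction.

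The results at stake are the comparison in 6.4(3) and the concomitant-treatment odds ratio in 6.4(4). Both are presented as evidence on what affects safety, and the odds ratio is intended for the re-examination report. Adjusting for baseline covariates does not repair an exposure that the outcome has created.

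**Working it through.** The plan gives no figure for this analysis, and the study-size section is not visible, so there is nothing to reproduce. The check asks what the planned analysis returns when concomitant drugs have no effect on AEs.

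**Inputs (all assumptions)**

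- b: share of patients with a concomitant drug not prompted by an AE, taken as equal in patients with and without AEs
- q: chance that an AE patient is given a drug because of the AE
- p: share of patients with an AE
- N: number of patients

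The two-sided 5% level is from SAP section 7. The choice of chi-square or Fisher's exact test is from SAP 6.4(3); Fisher's was used when an expected count fell below 5.

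**Cell probabilities with no true effect and undated status**

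| | AE | No AE |
|---|---|---|
| Status yes | p[b + (1−b)q] | (1−p)b |
| Status no | p(1−b)(1−q) | (1−p)(1−b) |

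In the cross-product ratio, p, (1−p) and (1−b) cancel:

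OR = [b + (1−b)q] / [b(1−q)]

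The numerator exceeds the denominator by b + q − bq − b + bq = q. Under these assumptions the OR is therefore above 1 whenever q > 0, whatever p and N are.

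**Apparent odds ratios (true value 1.00)**

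- b = 0.95, q = 0.2: 0.96/0.76 = 1.26
- b = 0.8, q = 0.2: 0.84/0.64 = 1.31
- b = 0.9, q = 0.5: 0.95/0.45 = 2.11
- b = 0.8, q = 0.5: 0.90/0.40 = 2.25
- b = 0.5, q = 0.8: 0.90/0.10 = 9.0

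As AE percentages, with b = 0.8, q = 0.5, p = 30%: status yes 0.27/(0.27 + 0.56) = 32.5%; status no 0.03/(0.03 + 0.14) = 17.6%.

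**Chance of a significant test with no true effect** (multinomial simulation, 40,000 runs per row)

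| b | q | p | N | Rejection |
|---|---|---|---|---|
| 0.95 | 0.2 | 10% | 500 | 1.3% |
| 0.95 | 0.2 | 10% | 1,000 | 4.1% |
| 0.95 | 0.2 | 30% | 500 | 6.3% |
| 0.95 | 0.2 | 30% | 1,000 | 9.5% |
| 0.90 | 0.2 | 10% | 500 | 4.2% |
| 0.90 | 0.2 | 10% | 1,000 | 7.2% |
| 0.90 | 0.2 | 30% | 500 | 9.7% |
| 0.90 | 0.2 | 30% | 1,000 | 15.6% |
| 0.8 | 0.2 | 30% | 1,000 | 31.6% |
| 0.9 | 0.5 | 30% | 1,000 | 77.5% |
| 0.8 | 0.5 | 10% | 500 | 39.2% |
| 0.8 | 0.5 | 30% | 1,000 | 98.4% |

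The lowest figures arise where the unexposed group is small and Fisher's test is conservative.

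**With status fixed at first dose**, q no longer enters. The OR is 1.00, and rejection is 5.1% at b = 0.8, p = 30%, N = 1,000.

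**The case against.** The term is undefined rather than wrongly defined. The CRF holds dates and purpose, so a careful analyst could separate AE treatment without being told. That is possible, but nothing in the plan requires it, and the literal reading includes those drugs.

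The size is unknown. Labelling allows combination with methotrexate or other DMARDs, so most patients may already be exposed. At b = 0.95 and p = 10%, simulated rejection with q = 0 is 2.9% (N = 500) and 4.2% (N = 1,000), so the 1.3% and 4.1% above show no inflation. This stands. High b limits false significance but does not remove the bias in the estimate: at b = 0.95 and q = 0.5 the OR is still about 2.05 (0.975/0.475).

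The formula is a crude odds ratio that assumes equal unrelated drug use in both groups. Patients who stop early because of an AE may have less time to accumulate other drugs. At b = 0.90 and q = 0.2, unrelated use of 87.5% in AE patients brings the OR back to 1.00, since 0.875 + 0.125 × 0.2 = 0.90. This is fair. It shows a second distortion from the same undated status, not a reason to keep it. The adjusted odds ratio was not computed.

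A baseline flag also drops drugs started later, some of which may interact with Xeljanz. That loss is real but modest. Finally, 6.4(4) is tied to the re-examination report, which SAP 2.2.2 and Protocol 7.2.3 have due by 01 July 2020, so for that item a change may come late.

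**Conclusion.** The concern holds. As written, SAP 6.4(3)–(4) let the outcome create the exposure, and no visible text in either document prevents it. If some AEs prompt a new drug in patients otherwise on none, and unrelated drug use does not differ by AE status, the odds ratio is biased upward. The size cannot be fixed from the documents, because b, q, p and N are all assumed. With b of 0.90 to 0.95 and q = 0.2, rejection is about 1% to 16%, part of that range showing no inflation; with b = 0.8 and q = 0.5 it is 39% to 98%. If status were analysed by ATC class, which the SAP leaves open, b would be lower for the classes used to treat AEs and the bias larger.

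The damage is confined to these secondary factor analyses. The primary AE incidence in 6.4(1) does not depend on this variable.

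**What to change.** In SAP 4.3 and 6.4(3)–(4), define concomitant treatment status for the test and the logistic model as yes if at least one concomitant treatment was started on or before the first dose of Xeljanz and was still ongoing at that dose, and no otherwise. Keep the all-medication summary in SAP 6.3 as a descriptive table only.

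The flag needs no new data: Protocol 7.2.5.4 already asks sites to "Record the start date and stop date (year/month/day) of the concomitant medication", and Protocol 7.2.5.3 records the Xeljanz start date. Fixing status at first dose is safer than counting drugs started before the AE. That rule would give AE patients a shorter window than patients without AEs, and so a bias in the other direction.

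The cost is one definition and one derived variable. A short rule for incomplete concomitant-drug dates should go with it, since SAP 5.1.2 covers only the treatment stop date. The downside is that drugs started later for reasons other than an AE are no longer tested as risk factors. If they are of interest, an analysis that excludes drugs whose recorded purpose is AE treatment could be added as a supplement.
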